## 6. DURATION / TIMELINE OF THE STUDY

Study start month and year: 07/2021

Enrollment close month and year: 07/2024

Study end month and year: 07/2026

The study will last 60 months. In the first three years we expect to enroll approximately 60 subjects in accordance with the inclusion criteria.

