## 4. PROCEDURES RELATING TO THE STUDY

### 4.1 Intervention

In collaboration with the Liver Transplant Unit of the Foundation, samples of discarded tissue from patients undergoing liver resection will be collected (both intra-tumoral and extra-tumoral tissues in the case of hepatocarcinoma) or taken from the whole liver post-transplant. This procedure will not entail any additional risk for the patient compared to the usual routine, nor will it reduce the availability of material for standard pathological analyses.

These samples will allow us to isolate cells (ovalocytes – liver progenitor cells) to generate organoids from normal liver tissue (cholecystectomy) and suspected NASH.

We plan to collect up to 20 independent samples per tissue type. The groups considered will be:

- organoids, cultures of sinusoidal stellate cells isolated from 20 patients with CC genotype (I148I)
- organoids, cultures of sinusoidal stellate cells isolated from 20 patients with CG genotype (I148M)
- organoids, cultures of sinusoidal stellate cells isolated from 20 patients with GG genotype

(M148M)

A blood sample (approximately 7 cc) will also be taken, in addition to those already scheduled during regular clinical checks, at the time of surgery or liver biopsy.

It is planned to share a portion of the liver biopsy samples for immunohistochemical analysis to be carried out at the Division of Medicine, Institute for Liver and Digestive Health, University College London, in collaboration with [name], in order to further evaluate the expression of PNPLA3 associated with liver disease, subject to the preparation of an appropriate MTA.

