## 7. STATISTICAL ANALYSIS

### 7.1 Sample size and data analysis

The sample size was estimated in view of achieving the two primary outcomes of the project.

Previously published works (24, 25, 26, 27) have shown that the generation efficiency of liver organoids is approximately 100% starting from surgical resections and 33% from biopsies (24, 25).

Considering these estimates, in order to isolate at least 20 independent organoid cultures of each type of condition of interest in our study, we estimate to recruit at least 30 donors for each genetic variant. The intent is to obtain replicates for the analyses with a sufficient representation of the different stages of liver damage (normal liver, inflammation/fibrosis and hepatocellular carcinoma) and to be able to map the impact of the main most common inherited genetic variants (present in at least 20% of individuals) in the population.

For the first primary outcome, the primary analyses will be conducted from single-individual cell cultures. Given the descriptive nature of mapping cellular phenotypes and gene expression, and the large number of organoids ( $>10^3$ ) and cells ( $>10^9$ ) from a single individual, we will have sufficient statistical power (>80%) to identify and analyze specific cellular subsets representing >1% of the overall population.

As regards the second primary outcome, although there are important limitations in the estimate inherent to the type of project and linked to the uncertainty regarding the final characteristics of the model that will be developed during the project, we expect to observe a progressive increase in the

presence and severity of the steatohepatitis phenotype in organoids with increased number of PNPLA3 I148M variants. In particular, we estimated that we could reach a statistical power of 95% (alpha 0.05, two-tailed test) to observe a frequency of steatohepatitis phenotype of 75% vs. 25% in assemblyloids with extreme PNPLA3 genotypes, homozygous for the at-risk variant vs. wild-type (20 cases vs. 20 controls), which is consistent with the increased risk observed in clinical cohorts (28).

Statistical analyses will be performed using JMP (SA, Cary, NC) and R (<https://www.r-project.org>) software and statistical comparisons will be made using the one-way ANOVA or chi-square test, where appropriate. P values < 0.05 will be considered statistically significant.

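### The 95% power for 20 GG vs 20 CC is not supported by about 60 donors: no rule fills the genotype groups, and the protocol's own culture yield leaves fewer than 20 per group

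*Protocol*

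**What the plan says.** Section 4.1 defines three groups by PNPLA3 genotype, each of 20 patients; the last is "organoids, cultures of sinusoidal stellate cells isolated from 20 patients with GG genotype". The CC and CG groups are worded the same way.

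Section 7.1 powers the second primary outcome on the two extreme genotypes, "homozygous for the at-risk variant vs. wild-type (20 cases vs. 20 controls". It states 95% power at two-sided alpha 0.05 for phenotype frequencies of 75% and 25%, and names one-way ANOVA or the chi-square test for comparisons. It puts organoid yield at about 100% from resections and 33% from biopsies. To reach at least 20 cultures per condition, it says "we estimate to recruit at least 30 donors for each genetic variant".

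Section 6 gives the total: "In the first three years we expect to enroll approximately 60 subjects in accordance with the inclusion criteria".

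The inclusion and exclusion criteria (sections 3.2 and 3.3) contain no genotype condition. Section 3.2 requires only that a DNA sample be available. The additional study blood sample is taken "at the time of surgery or liver biopsy" (section 4.1), and section 4.6 determines the genotype on DNA from peripheral blood. No allele frequency for rs738409 is given.

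**The concern.** The power statement needs 20 usable donors in each homozygote group. The enrolment figure equals 3 x 20, so it works only if the three genotypes arrive in equal numbers and every donor yields a culture. The protocol provides no mechanism for the first, and section 7.1 plans against the second.

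GG vs CC is the only comparison for which the protocol gives a power calculation. Its power is limited mainly by the smaller homozygote group. If that group is well short of 20, a null or imprecise result on the genotype effect would be read against a 95% power that the study never had.

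**Working it through.** **1. The stated figure.** Inputs from section 7.1: 0.75 vs 0.25, 20 per group, two-sided alpha 0.05. Each group's variance term is 0.75 x 0.25 = 0.1875.

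- Unpooled normal formula: Phi(0.5 / sqrt(2 x 0.1875/20) - 1.96) = Phi(3.65 - 1.96) = 95.5%. This reproduces the 95%.
- Pooled normal formula: Phi((0.5 - 1.96 x sqrt(2 x 0.25/20)) / sqrt(2 x 0.1875/20)) = 91.7%.
- Exact power of the uncorrected chi-square test, by enumerating both binomials: 90.1%. Fisher's exact test: 83.4%.

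So the like-for-like baseline for a true 20 vs 20 with the named test is 90%, not 95%.

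**2. Genotype counts from 60 donors.** Assumptions: enrolment without regard to genotype, Hardy-Weinberg proportions, G-allele frequency q. Expected counts are CC = 60(1-q)^2, CG = 120q(1-q), GG = 60q^2. An expected 20 in both homozygote groups needs q >= sqrt(1/3) = 0.577 and 1-q >= 0.577 together. Those would sum to at least 1.155, so no q satisfies both. The smaller homozygote group is largest at q = 0.5, where both are 60 x 0.25 = 15.

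**3. Power at those counts, every donor yielding a culture.** Exact powers use rounded counts; the unpooled formula uses expected counts.

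| q | Expected CC/CG/GG | Chance of >=20 CC and >=20 GG | Exact chi-square (Fisher) | Unpooled formula |
|---|---|---|---|---|
| 0.50 | 15/30/15 | 0.14% | 81% (68%) | 88.5% |
| 0.40 | 21.6/28.8/9.6 | 0.015% | 81% (71%) | 84.5% |
| 0.30 | 29.4/25.2/5.4 | 0.00001% | 63% (55%) | 69% |
| 0.25 | 33.8/22.5/3.8 | below 0.00001% | 61% (46%) | 56% |

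In the best case the genotype split costs about 9 points by the exact chi-square (90% to 81%) or 7 by the unpooled formula (95.5% to 88.5%). At q = 0.30 it costs about 27 points (90% to 63%).

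**4. Culture yield, with genotypes balanced.** Thirty donors for 20 cultures implies a yield of 20/30 = 2/3. Sixty donors then give 60 x 2/3 = 40 cultures, or 40/3 = 13.3 per genotype. Exact chi-square power at 13 vs 13 is 82%. At 13.3 per group the pooled formula gives 76% and the unpooled 85%. Exact power moves in steps at these sizes, so 82% at 13 vs 13 beside 81% at 15 vs 15 does not mean that the smaller design is better; the pooled formula orders them as expected (76% and 82%).

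**5. Both together.** At q = 0.50 and a 2/3 yield, 10 vs 10 remain: pooled power 62%, unpooled 73%. At q = 0.30, 19.6 CC and 3.6 GG remain: 46% and 52%.

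**6. Donor totals.** If each genetic variant means each PNPLA3 genotype, section 7.1 needs 3 x 30 = 90 donors, against about 60 in section 6. Moving to 90 would not settle the matter without selection: under the assumptions of step 2 and full yield, the chance of 20 in both homozygote groups is 56% at q = 0.50, 7.5% at 0.40 and 0.012% at 0.30. The number of people for an expected 20 GG is 20/q^2, which is 80, 125, 222 and 320 at q = 0.50, 0.40, 0.30 and 0.25, before culture failure.

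**The case against.** The strongest reply is that the protocol may intend selection by genotype. Section 7.1 speaks of recruiting a number of donors for each variant, section 4.1 defines the groups by genotype, and 3 x 20 = 60 matches section 6. Section 3.2 lists an available DNA sample separately from blood sampling, so early genotyping is possible. This stands in part: enrolment without regard to genotype is an inference, and the protocol simply does not say how the groups will be filled. A reader might infer that 20/20/20 from 60 donors is impossible; the document does not support that. It does not rescue the 95%, however, because balanced groups still lose a third of donors at the protocol's own yield.

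The Hardy-Weinberg model and the values of q are also assumptions. The donors mix suspected NASH, carcinoma, other lesions, healthy post-transplant biopsies and cholecystectomies, and section 1.1 links the variant to some of these conditions. Pooled sources need not follow one q, so actual counts could differ from the table.

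A reader might also attribute the whole drop from 95% to genotype supply. That would be wrong: part of it comes from the formula, since the named test gives 90% at 20 vs 20.

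Section 7.1 does admit limits in its estimate, but attributes them to the type of project and the model still to be developed, not to donor numbers.

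Finally, the cap of 20 samples per tissue type in section 4.1 should not be set against the minimum of 20 cultures per condition in section 7.1. The units differ, and the comparison has no bearing here.

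**Conclusion.** The power statement is wrong as written: the planned enrolment does not deliver it on either reading.

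- **Without genotype selection, Hardy-Weinberg assumed:** at best 15 vs 15 is expected, with at most about a 0.14% chance of 20 in both groups. Exact chi-square power is about 81% at q = 0.5 or 0.4, 63% at 0.3 and 61% at 0.25, before culture failure.
- **With genotypes balanced by selection:** about 13 cultures per group at the implied two-thirds yield, and about 82% power. This needs no genetic assumption.

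Both compare with 90% for a true 20 vs 20 by the same test. Sixty donors would supply 20/20/20 only if genotypes were balanced by selection and every donor gave a culture, for example if all tissue came from resections. The protocol states neither condition.

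**What to change.** In section 7.1, replace the 95% with power for the chi-square test at the genotype counts expected from the planned enrolment after culture yield, shown over a stated range of allele frequencies. Name the method of calculation. Make sections 4.1, 6 and 7.1 give one donor number, and say whether it counts people enrolled or cultures obtained.

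If selection by genotype is intended, state the rule, when the genotype is known relative to tissue processing, and how many people will be genotyped. Closing the CC and CG groups once full does not by itself yield 20 GG from 60 donors; it requires more people to be screened, of the order shown in step 6 of the working.

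The restatement costs only a less favourable power figure and needs no additional donors. Reaching 20 vs 20 in practice would cost more genotyping and, at the two-thirds yield, more donors.

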## PROJECT GANTT

| Intervention                                                         | Period (months) |       |       |       |
|----------------------------------------------------------------------|-----------------|-------|-------|-------|
|                                                                      | 1-12            | 13-24 | 25-36 | 37-60 |
| Enlistment                                                           | -               | -     | --    |       |
| Informed consent                                                     | -               | -     | -     |       |
| Criteria of inclusion/exclusion                                      | -               | -     | -     |       |
| Generation of organoids                                              | -               | -     | -     |       |
| Expression Evaluation
Genetics in organoids
hepatic            | --              | --    | --    |       |
| Evaluation of specifications
liver proteins
in liver organoids | --              | --    | --    |       |
| Differentiation to
hepatocytes of the                             | -               | --    | --    | -     |

| organoids                                                         |    |    |    |    |
|-------------------------------------------------------------------|----|----|----|----|
| Isolation and characterization of star cells                      | -- | -- | -- | -  |
| Generation of assemblyloids                                       | -  | -- | -- | -- |
| In vitro treatment with fatty acids, cholesterol and sugars, etc. | -  | -- | -- | -- |
| Therapeutic silencing PNPLA3 in assemblyloids                     | -  | -  | -  | -- |
| Correlation analysis data                                         |    | -  | -  | -  |

## 7. STATISTICAL ANALYSIS

### 7.1 Sample size and data analysis

The sample size was estimated in view of achieving the two primary outcomes of the project.

Previously published works (24, 25, 26, 27) have shown that the generation efficiency of liver organoids is approximately 100% starting from surgical resections and 33% from biopsies (24, 25).

Considering these estimates, in order to isolate at least 20 independent organoid cultures of each type of condition of interest in our study, we estimate to recruit at least 30 donors for each genetic variant. The intent is to obtain replicates for the analyses with a sufficient representation of the different stages of liver damage (normal liver, inflammation/fibrosis and hepatocellular carcinoma) and to be able to map the impact of the main most common inherited genetic variants (present in at least 20% of individuals) in the population.

For the first primary outcome, the primary analyses will be conducted from single-individual cell cultures. Given the descriptive nature of mapping cellular phenotypes and gene expression, and the large number of organoids ( $>10^3$ ) and cells ( $>10^9$ ) from a single individual, we will have sufficient statistical power (>80%) to identify and analyze specific cellular subsets representing >1% of the overall population.

As regards the second primary outcome, although there are important limitations in the estimate inherent to the type of project and linked to the uncertainty regarding the final characteristics of the model that will be developed during the project, we expect to observe a progressive increase in the

presence and severity of the steatohepatitis phenotype in organoids with increased number of PNPLA3 I148M variants. In particular, we estimated that we could reach a statistical power of 95% (alpha 0.05, two-tailed test) to observe a frequency of steatohepatitis phenotype of 75% vs. 25% in assemblyloids with extreme PNPLA3 genotypes, homozygous for the at-risk variant vs. wild-type (20 cases vs. 20 controls), which is consistent with the increased risk observed in clinical cohorts (28).

Statistical analyses will be performed using JMP (SA, Cary, NC) and R (<https://www.r-project.org>) software and statistical comparisons will be made using the one-way ANOVA or chi-square test, where appropriate. P values < 0.05 will be considered statistically significant.

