## 3.2 Inclusion criteria

Patients of legal age who have given consent to participate in the study will be included and will be listed for the following procedures:

- liver biopsy for suspected nonalcoholic steatohepatitis (NASH) at the time of diagnosis;
- liver resection for hepatocellular carcinoma or other liver lesions (including secondary lesions from other neoplasms and benign focal lesions, which will allow obtaining starting liver tissue

healthy);

- post-transplant healthy liver biopsies;
- cholecystectomies.

You will also be required:

- willingness to sign informed consent for the study
- availability of DNA sample for genetic analysis and clinical data,
- blood sampling for genetic and epigenetic analysis and analysis of non-coding RNAs (lncRNAs, miRNAs and circRNAs).

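### The step from 30 donors to 20 organoid cultures per genotype works only if about half or more of the donors are resections, and the protocol neither states nor enforces that mix

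*Protocol*

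**What the plan says.** Section 7.1 states that the "generation efficiency of liver organoids is approximately 100% starting from surgical resections and 33% from biopsies (24, 25". From these yields, "in order to isolate at least 20 independent organoid cultures of each type of condition of interest in our study", it concludes "we estimate to recruit at least 30 donors for each genetic variant". The next sentence says that the cultures should give a "sufficient representation of the different stages of liver damage (normal liver, inflammation/fibrosis and hepatocellular carcinoma" stages, with no number for any stage. The power statement in the same section uses 20 cases against 20 controls, defined by extreme PNPLA3 genotype.

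Section 4.1 adds "We plan to collect up to 20 independent samples per tissue type" and lists three groups of 20 patients by genotype (CC, CG, GG).

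On sources, section 3.2 lists "liver biopsy for suspected nonalcoholic steatohepatitis (NASH) at the time of diagnosis", "liver resection for hepatocellular carcinoma or other liver lesions", post-transplant healthy liver biopsies, and cholecystectomies. Section 4.1 says that "samples of discarded tissue from patients undergoing liver resection will be collected", or tissue taken from the whole liver after transplant, and that these samples will provide organoids from normal tissue and from suspected NASH.

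**The concern.** The two yields differ by a factor of three, so the cultures obtained from 30 donors depend strongly on how many of them are biopsied. Section 7.1 gives one answer without the input that determines it. Two of the four entry routes in section 3.2 are biopsies, and section 7.1 gives no yield for cholecystectomies.

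Two things are at stake. The first is the 20 cultures per genotype on which the 95% power statement rests. The second is the promise of at least 20 cultures for each condition. If *condition* means disease, the low-yield source may fall on NASH, the disease under study. The limit on samples in section 4.1 makes this harder to read, because an upper limit of 20 samples is set beside a lower limit of 20 cultures.

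**Working it through.** **Inputs.** Yield 1.00 (resection) and 0.33 (biopsy), target 20 cultures, 30 donors per genetic variant: all section 7.1. Limit of 20 samples per tissue type: section 4.1. Three genotypes: section 4.1, so 3 × 30 = 90 donors. The resection:biopsy mix is not given, so it is varied.

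**Reproducing the plan's figure.** With biopsy share *w*, mean yield = (1 − *w*) × 1.00 + *w* × 0.33. At *w* = 0.5 this is 0.665, and 20 / 0.665 = 30.1 donors. The stated 30 is therefore reproduced by an equal mix. That this mix was used is an inference.

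**Varying the mix.** Expected cultures = 30 × mean yield; donors needed = 20 / mean yield.

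| Biopsy share | Expected cultures from 30 donors | Donors for 20 cultures |
|---|---|---|
| 0 | 30.0 | 20.0 |
| one third | 23.3 | 25.8 |
| one half | 19.95 | 30.1 |
| two thirds | 16.6 | 36.1 |
| three quarters | 14.9 | 40.2 |
| all | 9.9 | 60.6 |

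These are expectations. With exactly 15 resections (all successful) and 15 independent biopsies, reaching 20 requires at least 5 successes, and P(Bin(15, 0.33) ≥ 5) = 0.585.

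**Effect on the genotype comparison.** The stated 95% is reproduced by the unpooled normal formula, power = Φ(0.5 / √(2 × 0.1875 / n) − 1.96), for 75% vs 25%. It gives 95.5% at n = 20, 88.5% at n = 15 (about three quarters biopsies) and 73.3% at n = 10 (all biopsies), counting one assembloid result per donor culture.

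**The limit in section 4.1.** Twenty samples at yield *y* give 20 × *y* cultures, which is below 20 for any *y* < 1. For a tissue obtained only by biopsy, 20 × 0.33 = 6.6, about 7.

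**NASH, on two assumptions** (*condition of interest* means disease; NASH comes only from biopsies).
- Biopsies needed for 20 NASH cultures: 20 / 0.33 = 60.6, about 61.
- Keeping 20 cultures in each genotype from 30 donors allows about 15 biopsies per genotype, or 45 of 90. If all are NASH, 45 × 0.33 = 14.9, about 15 over all genotypes (15 × 0.33 = about 5 per genotype).
- Taking 61 of the 90 as biopsies leaves 29 resections: 29 + 61 × 0.33 = 49.1 cultures, or 16.4 per genotype. Both targets cannot be met with 90 donors.

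**The case against.** The strongest reply is that *condition of interest* means genotype. The same sentence of section 7.1 counts donors per genetic variant, section 4.1 defines its groups by genotype, and the power statement compares genotypes. On that reading an equal mix of 30 donors does give about 20 cultures, and disease stages are promised only sufficient representation. The figure of 30 is also a minimum, so more donors could be recruited. This stands as far as it goes, but the genotype reading still needs the mix that the protocol omits.

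A reader might infer more: that NASH will receive 7 to 10 cultures instead of a stated 20. The documents do not support this.
- No section states 20 NASH cultures as such.
- Section 4.1 says resection or whole-liver samples will also yield suspected-NASH organoids, and section 3.2 does not restrict resection donors to people without NASH.
- The range 7 to 10 supposes that all 20 samples, or all 30 donors of one genotype, are NASH biopsies. It mixes a per-genotype count with a limit that may be study-wide.

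A reader might also infer that a shortage of NASH donors lowers the stated power. It does not do so directly, because the comparison is by genotype and section 4.5 induces the phenotype in vitro. The comparison of physiological with NASH cells is a descriptive secondary endpoint with no stated size, so there is no target against which to measure a loss.

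**Conclusion.** The concern holds in a limited form. The step from 30 donors to 20 cultures is sound only at about half resections or more. At two thirds biopsies it falls to 16.6 per genotype and at all biopsies to 9.9, and the protocol does not prevent either. The limit of 20 samples per tissue type cannot deliver at least 20 cultures from any tissue with a yield below 100%. Sections 3.2 and 4.1 disagree on where NASH tissue comes from.

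The NASH figures (about 61 biopsies for 20 cultures; about 15 cultures at most from 90 donors with 20 kept per genotype) are conditional on the disease reading and on a biopsy-only source. All results take the two cited yields at face value. The problem remains even if all 90 donors are enrolled; that section 6 expects about 60 subjects is a separate discrepancy.

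**What to change.** In section 7.1:
- State the mix that the 30-for-20 step requires (at least about half resections in each genotype), or restate the expected cultures per genotype for the mix actually planned.
- Define *condition of interest* as genotype or as disease.
- Give expected cultures by source, and withdraw the promise of at least 20 for any condition obtained only by biopsy.

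Across sections:
- Reconcile the limit of 20 samples in section 4.1 with the minimum of 20 cultures in section 7.1, and say whether the limit applies per genotype or to the whole study.
- Reconcile the source of suspected-NASH tissue in section 3.2 with that in section 4.1.

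The cost is revised text and, if the mix is to be guaranteed, a count of donors by source during recruitment. The downside is that the stated culture numbers become slightly less favourable.

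### The donor and culture numbers in sections 4.1, 6 and 7.1 do not reconcile, so the stated enrolment does not secure the 95% power

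*Protocol*

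**What the plan says.** - **Section 7.1, yield and donors.** Organoid generation is taken to succeed in "approximately 100% starting from surgical resections and 33% from biopsies". On that basis, and to reach at least 20 independent cultures per condition, "we estimate to recruit at least 30 donors for each genetic variant".
- **Section 7.1, power.** For the second primary outcome the protocol claims 95% power (two-sided alpha 0.05) to see the steatohepatitis phenotype in 75% versus 25% of assembloids, "homozygous for the at-risk variant vs. wild-type (20 cases vs. 20 controls").
- **Section 4.1.** There are three groups, each with cultures from 20 patients: CC, CG and GG. The last entry reads "organoids, cultures of sinusoidal stellate cells isolated from 20 patients with GG genotype".
- **Section 6.** "In the first three years we expect to enroll approximately 60 subjects in accordance with the inclusion criteria". Recruitment then stops: "Enrollment close month and year: 07/2024".
- **Section 3.2.** The first route into the study is "liver biopsy for suspected nonalcoholic steatohepatitis (NASH) at the time of diagnosis". Resections, post-transplant biopsies and cholecystectomies are also admitted. No criterion refers to PNPLA3 genotype; a DNA sample need only be available.

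**The concern.** Section 7.1 inflates donors over cultures by half, because some cultures will fail. Section 6 shows no such inflation: its total equals the number of successful cultures that 4.1 lists. A reader therefore cannot tell whether the study needs about 60 donors or at least 90, or whether the 20 patients per group in 4.1 are people enrolled or cultures obtained.

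The power claim for the second primary outcome is at stake. It is conditional on 20 GG and 20 CC cultures, and the stated enrolment supplies these together with 20 CG only in the best case. An ethics committee also needs the true number, since each donor gives an additional blood sample.

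**Working it through.** **1. The stated power.** Inputs from 7.1: 0.75 versus 0.25, 20 per group, two-sided alpha 0.05. Unpooled normal approximation:

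power = Φ(0.5 / √(0.1875/20 + 0.1875/20) − 1.96) = Φ(3.651 − 1.960) = 95.5%.

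The 95% therefore reproduces at exactly 20 versus 20. For the chi-square test that 7.1 names, the exact power without continuity correction is 90.1%.

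**2. The implied yield.** 20 cultures from 30 donors is 20/30 = 0.667. With 100% success from resections and 33% from biopsies, 30 donors give 20 cultures when (20 − 30 × 0.33)/(1 − 0.33) = 15.1 are resections, about half. This mix is back-calculated and is not printed in the protocol.

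**3. Possible readings of a genetic variant in 7.1, against 4.1 and 6.**

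| Reading | Consequence |
|---|---|
| Each of three PNPLA3 genotypes | 3 × 30 = at least 90 donors, against about 60 |
| Only the two extreme genotypes | 2 × 30 = 60 donors, which matches section 6, but none is left for the 20 CG patients in 4.1 |
| Several genes, one donor counting more than once | The 90-versus-60 clash goes, but 4.1 still lists 3 × 20 = 60 cultures, and 60 × 0.667 = 40 |

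The third reading has support: 7.1 speaks of the "main most common inherited genetic variants (present in at least 20% of individuals"), and section 5.1 names TM6SF2, MBOAT7 and GCKR. It does not help with 4.1, because CC, CG and GG exclude each other. If instead the 20 patients in 4.1 are enrolled donors, the total of 60 fits, but then 20 cultures per condition requires that nothing fails.

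**4. What 60 donors deliver.** Assumptions: an even 20/20/20 split, and one donor = one culture = one assembloid model (section 5.1 also plans genotype combinations). With resection share s, expected cultures per genotype = 20 × (s + 0.33 × (1 − s)). Donors needed for 60 cultures = 60 / (s + 0.33 × (1 − s)).

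| Resection share | Cultures per genotype | Donors needed for 60 cultures |
|---|---|---|
| 100% | 20 | 60 |
| 75% | 16.7 | about 72 |
| 50% | 13.3 | about 90 |
| 25% | 10.0 | about 121 |
| 0% | 6.6 | about 182 |

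**5. Power at those sizes** (75% versus 25%, two-sided 0.05).

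| GG vs CC | Unpooled formula | Exact uncorrected chi-square |
|---|---|---|
| 20 vs 20 | 95.5% | 90.1% |
| 19 vs 19 | 94.5% | 89.8% |
| 17 vs 17 | 92.0% | 88.1% |
| 13 vs 13 | 83.7% | 82.0% |
| 10 vs 10 | 73.3% | 61.9% |
| 7 vs 7 | 57.9% | 52.1% |
| 10 vs 20 | 84.7% | 78.4% |
| 7 vs 13 | 69.3% | 62.5% |

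The uneven rows are examples only. Exact power does not rise steadily with group size (18 vs 18 gives 90.8%, above 20 vs 20), so small differences in the last column mean little.

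**The case against.** The best defence is the two-group reading. Thirty donors for each extreme genotype make 60, which matches section 6, and at a two-thirds yield they give the 20 versus 20 behind the 95%. Only CG is then unprovided for, and the power statement does not use CG. This stands as far as it goes. But it contradicts 4.1, and it would require enrolment selected by genotype, which the criteria do not provide.

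Second, 4.1 introduces its groups with a ceiling of 20 samples per tissue type, so 20 per genotype may not be a firm requirement. That ceiling is by tissue, not genotype, and could only lower the numbers. The power calculation still needs 20 and 20.

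Third, 4.1 describes the tissue mainly as discarded resection or post-transplant liver, so a high yield is plausible. This makes the lowest rows of the tables less likely. It does not remove the eligible biopsies, and 7.1's own 30-for-20 allowance assumes failures.

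Fourth, the protocol admits limits to its estimate, and section 6 says its total is approximate. The admitted uncertainty concerns the final form of the model, not donor numbers, and an approximate total does not cover a gap of 30 donors or 20 cultures.

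Finally, no printed calculation is wrong, and the choice of power formula is a separate matter from donor numbers. Both points are fair. The defect is that the sections contradict each other, and the donor shortfall appears under either formula.

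**Conclusion.** The concern holds. Under no reading that allows for culture failure do 4.1, 6 and 7.1 agree. The 95% is correct arithmetic for 20 versus 20, but about 60 donors give those groups together with 20 CG only if nearly all tissue comes from resections and the genotypes split 20/20/20. The protocol secures neither.

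The shortfall is about 30 donors on the three-genotype reading, or about 20 cultures at 7.1's own yield. With that yield and an even split, power for GG versus CC is about 84% (unpooled) or 82% (exact), at 13 per group. In the best case nothing is lost. With few resections or an uneven split, power could fall well below 80%. Figures away from 20 versus 20 are illustrations that rest on one assembloid model per donor and on the mixes and splits shown, which the protocol does not give.

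**What to change.** 1. Use one set of donor and culture numbers in 4.1, 6 and 7.1.
2. Define what a genetic variant covers in the 30-donor statement, and say whether the 20 patients per group in 4.1 are enrolled donors or successful cultures.
3. State the expected resection/biopsy mix and the expected genotype split.
4. Then choose one course. If the larger number is intended, correct the total in section 6. Otherwise keep about 60 and replace the 95% with the power, or a range, for the GG and CC cultures actually expected, calculated for the chi-square test that 7.1 names.

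This costs wording and one recalculation. Raising enrolment is not required. If a larger number was intended, recruiting it would take more donors or more time.
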